#### 11.2.2. Retreatment Plan

Catheter implantation (section 11.1.1), PVSRIPO infusion at dose level -1 (section 11.1.2), gadolinium distribution quantitation (section 11.1.3), and biopsy sampling (section 11.1.4) will occur according to the procedures previously described in this protocol. In addition to the PVSRIPO retreat infusion, the patients will also receive a single dose of lomustine at approximately 8 weeks post-infusion of PVSRIPO. All procedures previously described will be followed; however, the addition of the single dose of lomustine will alter the schedule of events that was previously described. All retreated patients will follow the schedule of events shown in Table 6 and described in section 12.

#### 11.3. HISTORICAL MODIFICATIONS TO THE PROTOCOL

#### 11.3.1. Study Design Modifications (11/15/2013 AMD025)

As of 11/15/2013, 4 patients have been treated on dose level 5. One patient experienced a DLT upon removal of the treatment catheter. The remaining 3 patients have not experienced a DLT; however, all 3 have had difficulties tapering off steroids. To address this concern, the study is amended to reduce the dose for the next cohort of patients to dose level 2. Up to 6 patients will be accrued at dose level 2. If 2 of these patients experience a DLT as defined in section 11.4, accrual will be suspended. Following a two-week observation period, during which the patient will be evaluated in clinic on day 7 ( $\pm$  2 days) and day 14 ( $\pm$  2 days), a patient summary will be prepared and submitted to the DSMB chair for approval. Once approval from the DSMB chair has been obtained, treatment of the next patient will be allowed. Only one patient will be treated every 2 weeks and there will be only one PVSRIPO treatment per patient without specific approval for a second or more treatments from the FDA and the IRB.

#### 11.3.2. Study Design Modifications (6/05/2014 AMD041)

As of 06/05/2014, 5 subjects have been treated on dose level 2. Four subjects have completed the two-week follow-up period and have not had a DLT. One subject remains in the 14 day follow up period. Once one last patient has been treated, the study per the November 2013 amendment is complete. We are amending the study to allow continued patient accrual to garner more information about patient safety while the single-institution phase 2 study is being developed and reviewed by various regulatory bodies. We intend to continue accruing subjects for treatment at dose level 2 until such time that the phase 2 study has been activated. After each patient has been followed for a one-week observation period, during which the patient will have been evaluated in clinic on day 7 ( $\pm$  2 days), a patient summary will be prepared and submitted to the DSMB chair for approval. Once approval from the DSMB chair has been obtained, treatment of the next patient will be allowed. We will treat up to four subjects within a 30-day period as allowed by DSMB chair, and there will be only one PVSRIPO treatment per patient without specific approval for a second or more treatments from the FDA and the IRB.

#### 11.3.3. Study Design Modifications (10/06/2014 AMD048)

As of 10/06/2014, 7 subjects have been treated on protocol at dose level 2. One additional subject has been treated under a Single Subject Emergency Use Request at dose level 2. Of these eight subjects, six subjects had difficulty or remained unable to be tapered off steroids more than three months post infusion (three subjects required the addition of bevacizumab to facilitate the taper down or off steroids). We are amending the study to reduce the dose to dose level -1 (5.0 X  $10^7$  TCID50) with the goal of limiting the occurrence of known possible side effects of prolonged steroid use in patients who otherwise benefit from this investigational therapy. This dose reduction will allow continued patient accrual and garner more information about patient safety and optimal dosing while the singleinstitution phase 2 study is being developed and reviewed by various regulatory bodies. Our last amendment allowed the enrollment of up to 18 patients, one patient was enrolled under that amendment and thus, we are planning to enroll up to 17 patients on dose level -1. After each patient has been followed for a one-week observation period, during which the patient will have been evaluated in clinic on day 7 (± 2 days), a patient summary will be prepared and submitted to the DSMB chair for approval. Once approval from the DSMB chair has been obtained, treatment of the next patient will be allowed. We will treat up to four subjects within a 30-day period as allowed by DSMB chair, and there will be only one PVSRIPO treatment per patient without specific approval for a second or more treatments from the FDA and the IRB.

#### 11.3.4. Study Design Modifications (1/13/2015 AMD054)

Once the optimal dose level of PVSRIPO is determined, a total of 26 patients will be treated at that dose level, on a dose expansion cohort. The survival associated with these 26 patients will be compared to that of a historical cohort (see section 14.3). The study is being amended to allow accrual and treatment of a total of 26 patients at the optimal dose level of PVSRIPO and, as needed, radiation-necrosis dose levels and schedules of bevacizumab to estimate the efficacy of PVSRIPO relative to a historical cohort.

#### 11.3.5. Sample Size Modification (6/24/2015 AMD071)

As of 6/24/15, we have treated 13 patients on dose level -1. None of the patients have had prolonged steroid needs, two patients died at 3 and 6 months respectively, and five patients total (including the two patients who died) were initiated on bevacizumab. It is now felt that dose level -1 is the optimal dose, as none of the patients have experienced undue side effects due to PVSRIPO or the management of the cerebral inflammation secondary to PVSRIPO. We are now amending the protocol to enroll a total of 50 patients on dose level -1.

#### 11.3.6. Study Design Modification (11/10/2015 AMD078)

Imaging response criteria were previously developed based on imaging observations following chemoradiation treatment (Macdonald criteria) and subsequently revised based on new observations from anti-angiogenic trials (RANO criteria). As imaging is dramatically different following treatment with immunotherapy, new imaging criteria are being developed (iRANO). This process is likely to take several years to validate. For that reason, we are removing response rate as a secondary objective and adding, as an exploratory objective, a description of changes visualized on imaging due to intratumoral inoculation of PVSRIPO.

#### 11.3.7. Study Design Modification (2/1/2016 AMD081)

The protocol has been re-formatted in an electronic Common Technical Document (eCTD) format for electronic submission to the FDA for the associated IND. The statistical section has been revised and an appendix (section 18.4) has been added to define and describe the historical control group being used as a statistical comparison for the subject population. We have also further described the types of subject follow-up activity that will occur in this study.

Furthermore, patients previously treated on trial received high dose steroids prior to catheter insertion and throughout the infusion, as part of undergoing biopsy. Given concerns for negative impact of high dose steroids on the efficacy of PVSRIPO, we will limit steroid usage to the minimal dose necessary, if even needed.

#### 11.3.9. Study Design Modification (6/29/2016 AMD101)

This amendment includes several revisions to tests and procedures, which we believe can be safely implemented with the aim of reducing the time between consenting to participate in the study, screening to determine eligibility, and study treatment. Previously, patients had to demonstrate a serum total IgG level of  $\geq$  400 mg/dL to be eligible for the study. All patients who have undergone this testing thus far have met this eligibility criterion; therefore, it is no longer considered necessary to test serum IgG in patients going forward prior to their enrollment. We are also changing the timing of the boost immunization with trivalent inactivated IPOL™ (Sanofi-Pasteur) from between 6 months and 2 weeks prior to PVSRIPO infusion to between 6 months and 1 week prior to PVSRIPO infusion. Also, for previously enrolled patients, a patient had to be followed for a one-week observation period post-infusion, before the next patient could be treated. Now, once a subject has been observed through successful completion of the PVSRIPO infusion, the next subject We are updating pharmacy instructions for the preparation and can be treated. administration of PVSRIPO in this amendment as well. Lastly, per Duke's Research Integrity Office (RIO), a study-specific DSMB may no longer be necessary for this study given the oversight provided by the BTC's DSMB-Plus. If the FDA concurs, the studyspecific DSMB may be dissolved per its charter.

#### 11.3.10. Study Design Modification (9/5/2016 AMD104)

This amendment includes the addition of an exploratory objective to identify genetic predictors of response or failure of response to treatment with PVSRIPO. Molecular genetic tests, such as, but not limited to, DNA sequencing, gene amplification, and gene expression, will be performed on the tissue obtained at the protocol-specified biopsy prior to PVSRIPO infusion. Tissue may be obtained for testing as either fresh, frozen, or fixed tissue, or as slides, after the diagnostic pathologist has retained all tissue needed for diagnosis. The amount of tissue required for this testing should be sufficient to yield a minimum of one microgram of DNA.

#### 11.3.11. Study Design Modification (3/1/2017 AMD124)

Based upon recent pre-clinical data and clinical data collected on dose levels -1 and -2, we have concluded that there is no evidence of pre-clinically or clinically important differences between these dose levels. The initial need for treatment with the radiation necrosis dose levels and schedules of bevacizumab for cerebral inflammation secondary to PVSRIPO or tumor growth has been comparable thus far. In addition, the toxicity

profiles for the two dose levels are also similar. Therefore, we have decided to proceed with the development of PVSRIPO dose level -1 (5.0 X 10^7 TCID50) within the phase II study that is now in development. We are amending this phase I study to treat all future patients at the -1 dose level. We intend to continue accruing patients and treating patients at this dose level while the phase II study is being finalized and reviewed by various regulatory bodies.

This protocol is also being modified to allow multiple patients to be infused with study drug simultaneously if the neuro-surgical schedule allows. There are currently 3 neurosurgeons listed as sub-investigators who are trained on the surgical procedures for this study. In the study modification dated 6/29/2016, the study was modified so that the next patient could be treated immediately following the completed infusion of the previous patient. However, we would like to increase our enrollment potential by allowing multiple patients to be treated simultaneously. As of 1/20/2017, no patients have experienced complications during the infusion of PVSRIPO. Only 1 out of 51 treated patients has experienced severe complications (Grade III or higher) during catheter removal following the infusion of the study drug, and therefore we are confident that treating multiple patients would be safe for the patients and would allow for increased data collection.

This amendment also includes updates to the program used for planning catheter placement, the timing of catheter removal, the infusion pump information, and to clarify the history of DLT monitoring in the study. The statement related to sending MRIs to Therataxis was modified to state that the MRIs may be sent to Therataxis. A clarification has been made regarding the blood test for anti-epileptics. Lastly, the exclusion criterion related to completion of standard of care treatments has been clarified based on whether or not the MGMT promotor methylation status is known at the time of screening. There are other minor corrections throughout.

Following the FDA's review of this amendment, an additional section (see section 11.5) describing guidelines and criteria for study pause as a result of toxicity monitoring has been added. Specifically, the study is being monitored for the occurrence of unacceptable toxicities within dose levels -1 and -2 at any time after the initiation of protocol treatment.

#### 11.3.12. Study Design Modification (6/22/2017 AMD142)

It has been recently observed that patients who originally benefitted from the infusion of PVSRIPO can demonstrate tumor recurrence years later. Given the limited life expectancy of recurrent glioblastoma patients, it has been hypothesized that retreatment of long-term survivors previously treated with PVSRIPO could trigger an immune recall effect and thus further extend the survival of patients. As such, in the current amendment, we will allow selected patients who have previously benefited from PVSRIPO infusion to be retreated with PVSRIPO in the event of tumor recurrence. A patient is considered to have benefited from the initial PVSRIPO infusion if they survived 12 or more months after PVSRIPO treatment. All patients retreated will be treated at dose level -1 as per the same procedure previously used. Furthermore, all retreated patients will receive a single dose of lomustine 8 weeks post infusion of PVSRIPO. As lomustine temporarily reduces the number of regulatory T-cells, it is hypothesized that it could potentially increase the efficacy of PVSRIPO and of the immune recall. Further details regarding this retreatment plan are in Section 11.2.

#### 11.3.13. Study Design Modification (9/25/2017 AMD149)

Based upon the Final Clinical Shedding Study for PVSRIPO (IND 14,735) dated 8/6/2017, the IBC reviewed the requirement for stool sampling for patients receiving investigational treatment with PVSRIPO. The purpose of the stool sampling was to test for presence of Page 30 of 64

viral shedding in stool samples of patients receiving PVSRIPO via intracerebral delivery. The Final Clinical Shedding Report indicates no presence of PVSRIPO in stool collected from 59 subjects who received 61 treatments with PVSRIPO (2 patients were re-treated). Per the report, "we feel that the serologic evidence indicates a formidable protective shield against shedding in patients with pre-existing and boosted anti-polio immunity." On 8/17/2017, the IBC determined that the requirement for viral shedding studies may be discontinued on the basis of the report. Therefore, we have removed stool sampling from Section 12.2 and from Table 6. In addition, we have added 3 additional biopsy core samples to be taken at the time of biopsy, prior to catheter placement, if possible. The additional biopsy core samples will be used for genetic analysis, including full genome or full exome sequencing, as well as other molecular genetic testing.

### **11.4. DOSE-LIMITING TOXICITY**

Patients will be monitored for toxicity indefinitely or until confirmation of recurrent disease or the patient prematurely discontinues from the study at Duke University Medical Center. Adverse events will be categorized and graded in accordance with the NCI CTC (Version 4).

During the dose escalation phase of this study, patients were also monitored for dose-limiting toxicity (DLT). As no patient experienced a DLT on dose level 2, dose level 2 was determined to be the MTD. On 10/06/2014, the protocol was amended to reduce the dose to dose level -1 (see section 11.3.3). Since dose level 2 was determined to be the MTD, DLT monitoring was discontinued at that time.

With the removal of oversight by the study-specific DSMB, a patient summary with toxicity review will no longer need to be generated after each patient (see section 11.3.9).

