#### 11.1.5.1. Rules for Escalation

We propose adopting a phase I escalation strategy that avoids well-publicized shortcomings of standard '3+3' designs, in particular the problem of 'memory loss' with such designs (40). To minimize the number of patients treated at low-dose levels, minimize the number of patients needed to complete the study and efficiently use accumulated data to evaluate the appropriateness of dose escalation (40, 41), we plan to use a two-step continual reassessment method (CRM) design that includes an escalation step and a model-guided step (42, 43). In the escalation step, dose levels will be rapidly escalated as preclinical data suggest that dose-limiting toxicity (DLT) will not occur at any of the five dose levels that will be evaluated (44). Decisions concerning dose escalation for subsequent patients will be based upon the occurrence of DLT during the first 4 weeks after treatment administration. Initially, each patient will be observed for  $\geq$ 4 weeks before the next patient is treated. Starting at dose level 1, one patient will be treated at each higher dose level (Table 3). If no DLT is observed within 4 weeks of administration, then the next patient will be treated at the next higher dose. If no DLTs are observed among patients treated on the first four dose levels, subsequent patients will be treated at dose level 5. The escalation step will be interrupted if a patient assigned to one of the first 4 dose levels or more than 20% of patients treated at dose level 5 experiences a DLT. In that case, further dose escalation or de-escalation will be guided by the likelihood-based implementation of the CRM, in which the one-parameter hyperbolic tangent model will be used to estimate the probability of DLT at each of the 5 dose levels based upon available data (45). The highest dose level for which this estimated probability is less than 20% will be identified. If this optimal dose is less than or the same as the current dose, subsequent patients will be treated at that dose level. If greater than the current dose, subsequent patients will be treated at the one dose level higher than the current dose. The optimal dose will be recomputed whenever the status of DLT has been determined for a patient.

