As more patients are treated with PVSRIPO the impact of a DLT on subsequent patient treatment assignments by the model described above will decrease with the expectation that treatment assignments will stabilize over time at a particular dose level. If the outcome (i.e. DLT or not DLT) of a particular patient has no impact upon treatment assignment for the subsequent patient or patients, a 4-week observation period will not be required before accruing that additional patient or patients.

For example, consider the situation where one patient has already been treated at each of the first 4 dose levels without DLT and 4 patients have been treated at dose level 5 without DLT. Under the model described above, a 5th patient would be treated on dose level 5. If this 5th patient experiences a DLT, the treatment assignment for the subsequent patient would be dose level 5 according to the rules described above. If this 5th patient does not experience a DLT, the subsequent treatment would also be dose level 5. Hence, a 4-week observation period for the 5th patient on dose level 5 is unnecessary to determine the dose treatment assignment for the following patient. In this case, a 4-week observation period for the 5th patient will not be required as it has no impact upon treatment assignment for the subsequent for the subsequent patient.

The clinical team will keep the statistical team apprised of the current status of all patients. The statistical team will determine and inform clinical investigators as to whether a 4-week observation period is required for some or all patients before another patient is accrued. More specifically, based upon the rules described above, the statistical team will inform Page 25 of 64 clinical investigators as to how many patients can be accrued while other patients are within their 4-week post-treatment observation period.

Dose Level	PVSRIPO dose	Anticipated No. of patients treated in original design*	Administration route
1	1.0 x 10  TCID50	1	intratumoral
2	3.3 x 10  TCID50	1	intratumoral
3	1.0 x 10  TCID50	1	intratumoral
4	3.3 x 10  TCID50	1	intratumoral
5	1.0 x 10  TCID50	21	intratumoral

Table 3. Dose escalation schedule for PVSRIPO

\*Please refer to study design modifications below.

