### 14. STATISTICAL CONSIDERATIONS

### 14.1. SAFETY AND DOSE-FINDING COMPONENT

The dose-escalation criteria as outlined above in section 11.1.5 will be used to determine the MTD of PVSRIPO.

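### Section 11.4 calls dose level 2 the MTD because no DLT occurred there; that cannot identify a maximum, and the rule cited in 14.1 would not return level 2

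*Combined protocol and SAP*

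**What the plan says.** - **Objective.** Section 6.3.1 makes the MTD and the phase II dose the primary objective.
- **MTD rule.** Section 14.1: "The dose-escalation criteria as outlined above in section 11.1.5 will be used to determine the MTD of PVSRIPO". Section 11.1.5.1 escalates one patient at a time: "If no DLT is observed within 4 weeks of administration, then the next patient will be treated at the next higher dose". If a DLT occurs at levels 1 to 4, or in more than 20% of level 5 patients (the synopsis says 20% or more), a likelihood CRM with a one-parameter hyperbolic tangent model takes over: "The highest dose level for which this estimated probability is less than 20% will be identified".
- **Departure from the rule.** Section 11.3.1 (AMD025) reports four patients at level 5. One had a DLT at catheter removal, and the other three had trouble coming off steroids. It continues: "To address this concern, the study is amended to reduce the dose for the next cohort of patients to dose level 2". Up to six patients were allowed, with this safeguard: "If 2 of these patients experience a DLT as defined in section 11.4, accrual will be suspended". The Table 3 footnote points to the amendments: "Please refer to study design modifications below".
- **Next reduction.** Section 11.3.3 (AMD048, 10/06/2014) reports seven on-protocol patients at level 2 and one emergency-use patient. Six of these eight had prolonged steroid difficulty, and the dose was cut to level -1.
- **MTD declaration.** Section 11.4: "As no patient experienced a DLT on dose level 2, dose level 2 was determined to be the MTD". Sections 11.4 and 11.5 give this declaration as the reason DLT monitoring ended.

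**The concern.** A maximum tolerated dose needs evidence on both sides: the chosen dose is acceptable and the doses above it are not. Section 11.4 supplies only the first half. The patients at levels 3 and 4, both above level 2, must also have been free of DLT, because otherwise the escalation step would not have reached level 5.

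Two current statements also conflict. Section 14.1 says one rule determines the MTD, while 11.4 declares an MTD on a different ground. A reader of the final report would take level 2 to be a DLT-based ceiling. It is in fact a level with no observed DLT, reached because of steroid-taper difficulty at level 5. The label answers half of the primary objective and is the stated reason for ending DLT monitoring.

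**Working it through.** **Inputs**

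- Level 5: 1 DLT in 4 (11.3.1).
- Level 2: no DLT (11.4), with 7 treated on protocol by 10/06/2014 (11.3.3). These 7 are six under AMD025 and one under the next amendment, so the escalation patient appears to be an eighth.
- Levels 1, 3 and 4: 0 DLT in 1 each. This is inferred from the escalation rule.
- Cross-check: 14.3.1 gives 28 treated, 13 of them at level -1. 28 - 13 = 15 = 1 + 8 + 1 + 1 + 4.
- Skeleton: not given in the documents, so the check must hold for any increasing skeleton.

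**Model.** The hyperbolic tangent model has the form p_i = s_i^a with s_i increasing in dose. Put w_i = -ln s_i, so w_i/w5 ≥ 1 for levels 1 to 4. With one DLT, at level 5, and n5 patients there, setting the derivative of the log-likelihood to zero gives

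1 = (n5 - 1)·odds(p5) + Σ(i = 1 to 4) n_i·(w_i/w5)·odds(p_i)

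**Step 1: the protocol's own example.** Section 11.1.5.1 considers 0/1 at levels 1 to 4 and 1/5 at level 5, and concludes that "the treatment assignment for the subsequent patient would be dose level 5 according to the rules described above". Here 1 = 4·odds(p5) + positive terms. So odds(p5) < 0.25, p5 < 0.20, and the model selects level 5. Six assumed skeletons gave p5 from 0.114 to 0.197. The example is reproduced.

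**Step 2: the observed data.** 1/4 = 25% meets either version of the trigger, so the CRM step would have applied. With n5 = 4, suppose p4 ≥ 0.20. Then p5 ≥ 0.20 as well, both odds are at least 0.25, and the right-hand side is at least 3(0.25) + 1(0.25) = 1.00 before the positive terms for levels 1 to 3 are added. It therefore exceeds 1, a contradiction. So p4 < 0.20 for every increasing skeleton, and the rule returns level 4 or 5. More DLT-free patients at level 2 only add positive terms, so the result is the same for 0/7 or 0/8 there.

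Numerical confirmation, 15,000 random skeletons per count set:

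| Level 2 count | Rule returns level 4 | Rule returns level 5 | Rule returns level 2 |
|---|---|---|---|
| 0/1 (at AMD025) | 5,964 | 9,036 | 0 |
| 0/7 | 5,434 | 9,566 | 0 |
| 0/8 | 5,627 | 9,373 | 0 |

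The split between levels 4 and 5 depends on how skeletons are drawn and has no meaning of its own.

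**Step 3: sensitivity to the inferred patients** (0/8 at level 2, 4,000 random skeletons each). Dropping the level 3 patient gives level 2 in 0 fits. Dropping the level 4 patient gives level 3 in 79 and level 2 in 0. Dropping both gives level 2 in 2.

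**Step 4: what zero DLTs at level 2 shows.**

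- One-sided 95% upper limit: 1 - 0.05^(1/7) = 34.8% for 0/7; 1 - 0.05^(1/8) = 31.2% for 0/8.
- Chance of zero DLTs at a true 20% rate: 0.8^7 = 21.0%; 0.8^8 = 16.8%.

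**Step 5: the AMD025 rule is not an MTD criterion.** With six patients, the chance of 0 or 1 DLT (no suspension) is 0.8^6 + 6(0.2)(0.8^5) = 0.655 at a true 20% rate, and 0.7^6 + 6(0.3)(0.7^5) = 0.420 at 30%.

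**Step 6: steroid difficulty as the criterion.** This does not rescue the label. Six of 8 at level 2 had it, and the dose was then cut by 3.3×10^8 / 5.0×10^7 = 6.6-fold. This eight includes the emergency-use patient, so it is not the same eight as the inferred 0/8.

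**The case against.** The strongest reply is that AMD025 openly replaced CRM assignment, so a CRM fit to 8 to 15 patients is counterfactual. Section 11.1.5.1 also describes an optimum recomputed to place the next patient, under a design expecting 25 (Table 3), so such a fit is an interim recommendation. With the one-step cap, the patient after a clean level 2 cohort would go to level 3. All of this is fair, and it is why neither level 4 nor level 5 should be called the MTD. The evidence there is very thin: one inferred patient at level 4 (upper limit 95%) and 1/4 at level 5 (exact 95% interval 0.6% to 80.6%). But 14.1 is current text and names the 11.1.5 criteria as the way the MTD is determined, and AMD025 put no other MTD criterion in their place.

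A second reply is that little turns on the label. The phase II dose is level -1 on separate grounds (11.3.11), the reasons for the reductions are disclosed, and 11.5 keeps a 25% pause rule and six-monthly toxicity review. This also stands and limits the consequence to reporting. It does not make the declaration correct.

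Two smaller points are accepted. Steroid taper is not part of the DLT definition, so Step 6 only answers a possible defence of the label. AMD025 also reports the level 5 DLT just before the taper problem, so a corrected text should mention both.

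**Conclusion.** The concern holds. The only ground written in 11.4 shows that level 2 was tolerated in DLT terms. It does not show a maximum, and with 7 or 8 patients it does not exclude a DLT rate of 31% to 35%. The rule that 14.1 cites returns level 4 or 5 whatever the skeleton, given one DLT-free patient at level 4 and the catheter-removal event counted as a DLT, as the protocol counts it. If that event were not counted, there would be no DLT at any level and even less reason to stop at level 2. The counts at levels 1, 3 and 4 are inferred but agree with the total of 15. The effect is confined to the MTD half of the primary objective, the stated reason for ending DLT monitoring, and the pointer in 14.1. It should be fixed before the primary objective is reported.

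**What to change.** - **11.4, 11.5 and the primary-objective report:** state that no DLT-based MTD was established. Describe level 2 as a level with no observed DLT (0 in 7 to 8 patients, one-sided 95% upper limit about 31% to 35%). Say that it was adopted after 1 DLT in 4 at level 5, with steroid-taper difficulty in the other three as the concern AMD025 set out to address.
- **14.1:** say that AMD025 (11.3.1) superseded the CRM for dose assignment, and cite 11.3 alongside 11.1.5.
- **Report:** add one table of patients and DLTs by dose level with exact intervals. A CRM fit is optional, and only if the skeleton was specified in advance. Do not name level 4 or 5 as the MTD.

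The cost is a few reworded sentences and one table. No patients, dosing change or refit are required.
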